13.5 Exploratory analysis

The long-term risk of malignancies will be explored within a potential new cohort of MG patients who are treated with other FcRn antagonists, if sufficient patients can be identified for this patient cohort.

The study will also assess time to the first occurrence of malignancy overall and specified by type of malignancy using a Fine and Gray model in order to take into account a potential competitive risk for death and cumulative incidence curves will be provided. The index date will be the first claim of efgartigimod (for the efgartigimod cohort) or other MG treatment (for the reference cohort). The proportional hazards assumption will be checked using statistical tests and graphical diagnostics based on the cumulative sums of residuals. If the assumption is violated, an interaction term with time will be added in the model. The study will also assess the healthcare resource utilization (e.g., number of hospitalisations [including MG-related], ER visits, and MG exacerbations and crises) between the efgartigimod and reference cohorts. This exploratory analysis will be descriptive only; details will be provided in the SAP.

In order to assess the robustness of the results, a Proportional Hazard Model (Cox model) will be performed as a sensitivity analysis with providing cumulative incidence curves.

An exploratory analysis of the CPRD dataset (UK) to identify the extent of recorded MG related information will be performed and if feasible, analysis will be adjusted for disease severity.

13.6 Methods for addressing the potential for outcome misclassification in the claims databases

- Optum: to reduce the potential for false positive malignancy cases based on ICD-10 diagnosis codes in administrative claims database, an algorithm for malignancy case definition will be used that requires at least 2 malignancy diagnoses (within the same site) that are separated by ≥ 30 days.
- SNDS: the SNDS has becoming largely recognised by the French authorities as a powerful tool of pharmacoepidemiology and some guidance and algorithm have been published for the community and one in particular for cancer([Méthode | L'Assurance Maladie \(ameli.fr\)](#)).

14 Quality control

The SOP and work instructions of the sponsor's designated CRO will be used to guide the conduct of the study. These procedures include internal quality audits of the data, consistency of collected data, validation of coding, rules for secure and confidential data storage, methods to maintain and archive project documents, quality control procedures for programming, standards for writing analysis plans, and requirements for senior scientific review. Written programming will be reviewed independently. All key study documents, such as the SAP and study reports, will undergo quality control and senior scientific review.

The study will be executed in line with all applicable regulations and guidelines, such as the Guide on Methodological Standards in Pharmacoepidemiology, the European Network of Centres for Pharmacoepidemiology and Pharmacovigilance (ENCePP) Checklist for Study Protocols, and the International Society of Pharmacoepidemiology (ISPE) Guidelines for Good Pharmacoepidemiology Practices, as well as the data vendor's quality management system.

The SOP and work instructions of the MAH will be used to oversee the execution and conduct of the study by the CRO. These procedures include pre-qualification and in-process quality audits of the CRO's quality management software (QMS) and contracted services. Additionally, the Vendor Relationship Manual will be put in place and will include:

- Performance metrics
- Routine oversight activities
- CRO Governance meetings

The Vendor has SOPs in place which address the extent of source data verification, validation of endpoints, storage of records and archiving of the statistical programming performed to generate the results. These SOPs will be followed in this study.

15 Limitations of the research methods

This real-world observational study utilises data collected in administrative claims and EMR databases and is subject to limitations inherent to all database studies:

- There is no definitive coding algorithm to distinguish a generalized MG diagnosis vs. an ocular MG diagnosis in databases, although the indication for efgartigimod is specifically for patients with a gMG diagnosis. In this study, an algorithm for MG case ascertainment will be developed to identify the appropriate base cohort in the selected databases.
- Information concerning the malignancy may not be available in the selected claims databases such as Optum or SNDS. When evaluating risk of malignancies among patients with malignancy history, the study will not be able to distinguish if the current malignancy outcome is a new primary malignancy or a recurrence or metastases of the original primary malignancy.
- The lookback period is 1 to 3 years for the Optum database and up to 3 years for the EU and UK databases. However, this lookback period may not be sufficient to capture all important baseline data elements for this study. For instance, the possibility of obtaining the date of first diagnosis is low. In CPRD and SNDS, duration can be obtained if the first diagnosis is during the 3-year lookback period. However, if MG has been ongoing during the 3-year lookback period, duration of MG can only be given as >3 years. Limited continuous coverage for patients with MG in the Optum database may impact the study as follows:
 - Lack of continuity of coverage prior to a patient's study index date (efgartigimod initiation) may impact accurately evaluating:
 - Potential baseline confounders (e.g., thymectomy [date, indication, histology], thymoma [without thymectomy], malignancy history)
 - Duration of MG
 - Age at initial MG diagnosis
 - Treatment history (e.g., prior and baseline MG treatments)
 - Lack of continuity of coverage post drug initiation (efgartigimod or the reference drug) may impact ability to reliably evaluate risk of malignancy
 - Associated with repeated exposure to efgartigimod over time (e.g., dose, duration)
 - With a long latency period (e.g., 5+ years following efgartigimod initiation)
- Missing data are expected, particularly for certain covariates such as geography. Missingness will be assessed by comparing patients with missing data to those without missing data. The degree to which including or excluding those with

missingness may bias the findings will be estimated. This will also depend on the proportion of a given covariate that is missing. Methods such as multiple imputation may be needed if it is determined that their use may introduce bias.

- While Optum Market Clarity database is the largest insurer in the US covering over 100 million unique patients, it has a limited continuous coverage period for patients with MG according to a cohort study⁵ conducted among the MG patients in the Optum database.
- The primary use of the data from the three (3) selected databases is not for research purposes but to facilitate and record information relating to billing or patient management; therefore, available information only reflects what is pertinent to the primary use of the data rather than a meticulous record of every detail of testing or examination. However, the data sources of this PASS were selected based on a thorough evaluation of the variables to ensure complete and reliable capture of primary outcomes.
- Potential for misclassification of patient's exposure status can arise for several reasons in a retrospective database study:
- In an EMR database such as CPRD, prescription for a medication cannot guarantee that the patient has taken the medication. Therefore, the study may have misclassification of patients' exposure status.
 - Potential misclassification for patients exposed to efgartigimod before product launch (i.e., prevalent users):
 - In France, data on patients during the time they have been treated in the early access program will be available in the French SNDS database and hence will be included in the study as incident users. If a patient was exposed to efgartigimod in a clinical trial in France, the clinical trial exposure will not be captured in SNDS. If these patients are then exposed to commercial efgartigimod, the prior exposure in a clinical trial will not be captured and these patients will not be able to be identified as prevalent users.
 - In the UK, data from a patient exposed to efgartigimod in a clinical trial or in an Expanded Access/Compassionate Use Program may be present in the CPRD database if the electronic medical records for that patient are part of the data set and if the treating physician has recorded that the patient was exposed to efgartigimod. The CPRD database consists only of data from sites who have agreed to participate and is not

⁵ An internal position paper developed by argenx, titled "Malignancies with efgartigimod in generalized myasthenia gravis".

inclusive of all sites in the UK. Hence, it cannot be determined for certain if such patients will be included.

- As Optum is a US claims database, data during the time a patient was exposed to efgartigimod in a clinical trial is not included. Thus, there is the possibility of prevalent users not being identified. However, this is unavoidable when utilizing a claims database in the US.

Misclassifying prevalent efgartigimod users as new users would have the effect of inducing selection bias by retaining only healthy users and excluding those who discontinue treatment following early adverse events (depletion of susceptible). This could lead to an underestimation of cancer risk estimate. However, given that few patients have been enrolled in the efgartigimod clinical trials and early access programmes and that the UK EAMS (Early Access to Medicines Scheme) programme encourages patients to continue taking efgartigimod once it is marketed and reimbursed, as it was set up before efgartigimod was reimbursed, few patients should be affected by this issue. The effect of this potential selection bias on the point estimate is thus likely to be minimal.

- In claims databases such as Optum and SNDS, dispensing of oral medications are consolidated into a total pharmacy expense during an inpatient hospital stay, preventing the identification of any individual exposure during the visit. This potential for immeasurable time bias is primarily a concern for (1) hospital stays that last more than a few days and (2) oral treatments for MG that could impact malignancy risk. This potential source of misclassification will be addressed as follows:
 - Medication dispensing in the weeks prior to admission and following a discharge of a hospital visit with a length of stay that exceeds 1 week will be reviewed. If dispensing for a medication is observed in the prior or post hospitalisation period, then exposure to the same medication will be imputed to have occurred throughout the hospitalisation stay as well.
- Inability to control precisely for unmeasured confounders such as:
 - Severity of MG
 - Disease duration, which cannot be reliably measured in claims databases that represent patients' healthcare experience only during the time of enrolment in covered insurance plans. The date of the initial MG diagnosis may not be available due to limited *historical enrolment* prior to the study index date.
 - History of malignancy that may not have been identified in the databases
 - Lifestyle variables that are typically not available in the claims databases, or only intermittently collected in the EMR database(s)

- Other factors that may contribute to the cell mutation (e.g., genetic) as malignancy is a multifactorial disease
- There is potential for prevalent user bias in favour of the reference cohort that may result from prior use of non-efgartigimod MG therapies by patients in the efgartigimod cohort prior to initiating efgartigimod.
- Latency to cancer can only be estimated using models ([Nadler 2014](#)) and can range from 2 years to decades. It is therefore not possible to detect all types of cancer in an observational study.

16 Other aspects

N/A.

17 Protection of human subjects

This study will comply with scientific principles, EMA PASS study guidance document, the applicable guidelines ([GVP Module VIII](#)) ([EMA 2017](#)), the Declaration of Helsinki in the latest relevant version, and the applicable legal and regulatory requirements ([WMA 1964](#)).

Informed consent is not applicable for a database analysis study because only de-identified data will be used. Research using anonymised databases should not require Independent Ethics Committee (IEC) review and approval and specific patient authorisation for each use of the data ([ISPE Guidelines for GPP](#)).

The database providers will keep confidential any information provided by the Sponsor (including this protocol) related to this observational study and all data and records generated in the course of conducting the study, and will not use the information, data, or records for any purpose other than conducting the study. These restrictions do not apply to: 1) information which becomes publicly available through no fault of the database provider, 2) information which is necessary to disclose in confidence to an Institutional Review Board (IRB) solely for the evaluation of the study, or 3) study data which may be published.

18 Management and reporting of adverse events/adverse reactions

Given the information available within the Optum, CPRD and SNDS databases used for this study is deidentified, extraction of AEs data will not be conducted. Only data related to the study objectives (i.e., all events of malignancies) will be captured and summarised in interim safety analyses and final study report.

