9.4 Efgartigimod exposure definition and measurements

Efgartigimod is administered in cycles of 4 weekly administrations followed by an efgartigimod-free period. The initiation of the next cycle is based on clinical need.

This schedule of administration is based on results of clinical trials that showed that clinical response is following or even exceeding the duration of IgG reduction. Majority of patients receive 5-7 cycles per year which has been confirmed in real world studies ([Bhavaraju-Sanka 2024](#)).

In this study, a patient will be considered an efgartigimod exposed patient if he/she has received at least one (1) dose of efgartigimod. Exposure to efgartigimod IV and SC starts with the initial exposure date for the medication found in the patient record (patient's index date). It is determined that consecutive doses administered greater than 21 days apart will be considered a different cycle.

Based on these elements, the following treatment patterns will be identified:

- Ever used: patients who receive 1 administration to up to 1 cycle (ie., max. of 4 once weekly administration with less than 21 days between).
- Infrequent use: patients who have a *Medication Possession Ratio* (MPR) < 60%. MPR is defined as the sum of drug supply days covered by each cycle (28+21= 49 days) divided by the time elapsed between the first supply and the end of the follow-up period.
- Continuous use: patients who have received ≥ 2 subsequent cycles without any interruption of more than 120 days between cycles.
- Intermittent use: patients who have at least one interruption of more than 120 days between two consecutive cycles. If sample size permits, the intermittent group may be stratified according to MPR subclasses.

- Discontinuation is defined as a gap period of at least 120 days after the last claim/prescription/dispensing.

Additionally, taking into account the variable follow-up time and time interval between cycles, the following will be measured for efgartigimod:

- Number of administrations per year
- Total duration of the exposure
- Total number of administrations

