9.5 Outcomes

The study outcome of interest is long-term risk of malignancies in patients with MG initiating treatment with efgartigimod and MG patients not treated with efgartigimod, but are on any other therapy for the treatment of MG. Malignancies (examples mentioned in Table 1) will be identified in each of the study databases primarily by using coding algorithms based on International Classification of Disease. Currently Revision 10 is valid, however revisions of the ICD is expected and therefore the version valid at the time of analysis will be used. The algorithms may also consist of relevant procedure codes, and/or results from relevant laboratory tests whenever appropriate and available in the database. All final coding algorithms and detailed code lists will be provided in the SAP.

Table 1. Examples of types of malignancy to be collected, subject to the valid ICD version.

Event of interest	Types of Malignancy	Measurement
Malignancy	
 • Malignant neoplasms of lips, oral cavity and pharynx • Malignant neuroendocrine tumours • Secondary neuroendocrine tumours • Malignant neoplasms of digestive organs • Malignant neoplasms of respiratory and intrathoracic organs • Malignant neoplasms of bone and articular cartilage 	
Incidence rate of events of malignancy by type per patient-years exposed in the efgartigimod treated cohort compared to the reference cohort.
 
Incidence rate ratio and corresponding 95% CIs will be used to compare the malignancy events among the efgartigimod exposed cohort vs. the reference cohort. The calculations will be performed

	
 • Melanoma and other malignant neoplasms of skin • Malignant neoplasms of mesothelial and soft tissue • Malignant neoplasms of breast • Malignant neoplasms of female genital organs • Malignant neoplasms of male genital organs • Malignant neoplasms of urinary tract • Malignant neoplasms of eye, brain and other parts of central nervous system • Malignant neoplasms of thyroid and other endocrine glands • Malignant neoplasms of ill-defined, other secondary and unspecified sites • Malignant neoplasms of lymphoid, hematopoietic and related tissue • Thymic malignancies • In-situ carcinoma 	
separately for each individual database and across all three (3) databases as a meta-analysis according to published methods.

--	---	--

Abbreviation: CI = confidence interval.

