Each category of malignancy presented in [Table 1](#) will be assessed individually. If possible, adjudication through review of medical charts will occur for malignancy cases identified through coding algorithms in the claims databases used to conduct the study.

Outcome variables will include:

- Category of malignancy(ies)
- Date of malignancy diagnosis(ses) in a patient’s follow-up period

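### The Optum case rule has no route for a patient who dies or loses coverage before a second same-site code, so those cancers are counted as non-events

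*Protocol*

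**What the plan says.** Protocol Section 13.6 sets a claims rule for Optum, "to reduce the potential for false positive malignancy cases based on ICD-10 diagnosis codes in administrative claims database". The rule "requires at least 2 malignancy diagnoses (within the same site) that are separated by ≥ 30 days". It names no other way to qualify, and it does not say which of the two codes dates the event.

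Three other places bear on it:

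- Sections 9.2.2 and 13.2 end follow-up at death, loss to follow-up or the end of the study, and for reference patients also at a switch to efgartigimod.
- Section 9.5 says of the outcome algorithms in general: "The algorithms may also consist of relevant procedure codes, and/or results from relevant laboratory tests whenever appropriate and available in the database". It adds: "All final coding algorithms and detailed code lists will be provided in the SAP". On adjudication it says: "If possible, adjudication through review of medical charts will occur for malignancy cases identified through coding algorithms in the claims databases".
- Section 15 says of Optum that "it has a limited continuous coverage period for patients with MG". Section 11 assumes 50% exclusion there against 30% in the other two databases, partly because of higher loss to follow-up.

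The primary objective (Section 8) is restricted to patients without malignancy history in the lookback. The protocol does not state the code rule that defines history.

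**The concern.** The rule makes case status depend on what happens after diagnosis. The patient must be alive, covered and coded again at the same site at least 30 days later. Several codes during one terminal admission do not qualify if they all fall inside 30 days. The cancers most exposed are those that kill quickly, in a study whose purpose is cancer safety.

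The protocol states the benefit of the rule, fewer false positives, but not its cost in sensitivity. Section 15 does not mention that cost. The rule also applies in the database with the largest planned efgartigimod share and the weakest expected retention.

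Time to first malignancy is to be assessed "using a Fine and Gray model in order to take into account a potential competitive risk for death". There an unconfirmed cancer followed by death is recorded as a competing death without malignancy, and one followed by disenrolment as a censored patient.

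**Working it through.** **1. What happens to a first code on day 0**

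- Second same-site code on day 30 or later, while covered: a case.
- Death before such a code: not a case, and follow-up closes at death.
- Loss of coverage before such a code: not a case, and the patient is censored.
- Chart review in the second and third situations: not reached, because it is confined to algorithm-identified cases and is done only if possible.

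**2. The plan's own power figure**

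Inputs from Sections 9.1 and 11: background rate 0.042 per PY, 6 years, rate ratio 1.3, two-sided 5%, 2:1 matching, 679 unadjusted efgartigimod patients (679 × 2 = 1,358).

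- Variance of the log rate ratio = [1/(6 × 0.0546) + 1/(2 × 6 × 0.042)]/679 = (3.053 + 1.984)/679 = 0.00742, so SE = 0.0861.
- Power = Φ(ln 1.3/0.0861 − 1.96) = Φ(1.086) = 86.1%. Table 4 gives 86.13%.

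**3. Loss through disenrolment within 30 days**

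The documents give no disenrolment rate, so annual disenrolment d is assumed, independent of the cancer. Share lost = 1 − (1 − d)^(30/365).

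| d | share of cases lost |
|---|---|
| 10% | 0.9% |
| 20% | 1.8% |
| 30% | 2.9% |

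At the background rate, 600 Optum efgartigimod patients followed for 6 years give 600 × 0.042 × 6 = 151 expected cases, so the loss is about 1 to 4 cases. Early deaths add to this. The documents give no figure for them either.

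**4. If the missed share m is the same in both cohorts**

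Optum share = 600/1,599 = 37.5%. Pooled observed rate = 42.0 × (1 − 0.375m). The power formula in step 2 then gives:

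| m (assumed) | rate per 1,000 PY | power |
|---|---|---|
| 5% | 41.2 | 85.5% |
| 10% | 40.4 | 84.8% |
| 20% | 38.9 | 83.4% |
| 30% | 37.3 | 81.9% |

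The IRR is unbiased in every row.

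**5. If the missed share differs by cohort**

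Observed Optum IRR = true IRR × (1 − m_efg)/(1 − m_ref). For a true IRR of 1.30:

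- 20% missed with efgartigimod, 10% in reference: 1.30 × 0.80/0.90 = 1.16.
- 10% with efgartigimod, 20% in reference: 1.30 × 0.90/0.80 = 1.46.

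Weighting Optum by its 37.5% patient share on the log scale, the pooled values are 1.30 × (0.80/0.90)^0.375 = 1.24 and 1.30 × (0.90/0.80)^0.375 = 1.36. These missed shares only illustrate the sensitivity of the result; nothing in the documents supports any particular difference.

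**The case against.** The strongest reply is that Section 9.5 allows procedure codes and laboratory results in the algorithms and leaves their final form to the SAP, so the missing route may be supplied there. Optum Market Clarity also holds linked health-record data (Section 10.3), and Section 15 concedes that gaps in coverage after initiation may impair evaluation of malignancy. This stands in part. It would be wrong to say that the protocol as a whole excludes every alternative. But the Section 9.5 wording is permissive and does not say that anything may replace the second diagnosis, whereas the Optum sentence makes that diagnosis a requirement. An SAP that follows the protocol inherits it.

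The reply is also right on specificity. Accepting any single code that precedes disenrolment or the end of data in the main definition would readmit the rule-out codes the rule is meant to remove. False positives that are equal in both cohorts pull an IRR towards 1 and can hide harm.

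Three stronger readings are tempting but not supported:

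- *Cancers first coded just before index pass as incident.* This needs the two-code rule to define malignancy history too, or a pre-index code to pair with a post-index one. The protocol states neither. The planned sensitivity analysis that drops events in the first 12 months (Section 13.4) would largely expose such cases.
- *The rule pushes the IRR upward because efgartigimod patients have more contacts.* Section 9.4 does say "Majority of patients receive 5-7 cycles per year", which at 4 administrations a cycle is 20-28 a year. But a visit for MG treatment does not by itself produce a same-site cancer code, and reference patients may be on monoclonal antibodies as well as oral drugs (Section 9.3).
- *Every data cut loses its last 30 days of cancers.* Those at an interim cut can be confirmed at a later refresh; only the final cut loses them.

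**Conclusion.** The point holds in a limited form. As Section 13.6 is written, an Optum cancer followed by death or loss of coverage before a qualifying second code is never counted, and no other stated step recovers it. At an assumed 10-30% annual disenrolment, about 1-3% of Optum cases are lost to disenrolment within 30 days. To this is added an unknown share who die in that window.

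If the loss is equal in the two cohorts, the IRR is unbiased, and even 30% missed leaves power at 81.9%. If it is unequal, the Optum IRR can move in either direction, with a smaller effect on the pooled estimate. The documents settle neither the direction nor the size. Entry of prevalent cancers into the primary cohort is a possibility left open by the unstated history rule, not an established error. This is a worthwhile repair to a stated rule, not a threat to the design.

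**What to change.** In Section 13.6:

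1. Keep the two-code rule and add one route to the main definition: a first malignancy code followed by death before a second code could be recorded, within 30 days or another stated window.
2. Date the event at the first code and require that date to fall after index.
3. Add a sensitivity analysis that also accepts a single code followed by loss of coverage, or one supported by a cancer-treatment claim or an inpatient principal diagnosis. Report the strict two-code result alongside. The loss-of-coverage arm matters because Section 9.2.2 says ascertainment of deaths outside hospital differs by database, so some deaths may appear only as lost coverage.
4. State that the two-code rule does not apply to lookback history: any single pre-index malignancy code takes the patient out of the primary no-history cohort.

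The cost is a change of wording and extra runs on claims already held; data collection is not planned to start until September 2026. The downside is small: a few rule-out codes followed by death will be counted, and a few patients with a single lookback code will move to the history cohort.
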